10.3 Visit 3: Day 3-4

10.3.1 Tape and Polyester Chip Sites Irritation

Skin irritation due to the patch panel tape or chip will be evaluated and documented per the instructions presented in Section 10.2 Irritation that increases in severity or persists beyond visit 3 will be followed to resolution.

Tape Irritation will be evaluated according to the following score scale:

None: No erythema or other sign of irritation
Weak: Faint to definite pink erythema
Moderate: Moderate erythema, definite redness
Strong: Severe erythema, very intense redness

Polyester chip induced irritation will be evaluated according to the following score scale:

None: No erythema or other signs of irritation
Weak: Faint to definite pink erythema at **all** polyester chip sites*
Moderate: Moderate erythema, definite redness at **all** polyester chip sites*
Strong: Severe erythema, very intense redness at **all** polyester chip sites*

[figure not shown]
*To ensure that irritation resulting from skin contact with the polyester chip is not confused with an allergic response to a specific allergen, all of the polyester chip sites on each panel must present the same or nearly the same degree of irritation.

10.3.2 Allergic Skin Responses

Allergen site reactions will be evaluated for the presence of erythema, infiltration, papules, discrete vesicles and bullous reactions. These criteria will be used to score skin reactions according to standard patch testing guidelines established by the International Contact Dermatitis Research Group as discussed and shown below.

Skin reactions at test sites will be scored as: (Neg) negative; (IR) irritant reaction; (?) doubtful reaction; (1+) weak positive reaction; (2+) strong positive reaction; or (3+) extreme positive reaction.

Figure 6: Reaction Criteria

Notation Description Interpretation

Neg	Negative, no skin changes in the tested area,
?+	Faint, non-palpable erythema, possibly few papules
+(1+)	Palpable erythema, moderate edema or infiltrate, possibly few papules, no vesicles. Weak reaction.
++ (2+)	Strong infiltrate, numerous papules, possibly few vesicles present. Strong reaction.
+++ (3+)	Coalescing vesicles, bullae or ulceration. Extreme reaction.
IR	Inflammation sharply limited to the exposed area, lack of infiltrate, small petechiae, pustules, and efflorescences other than papules and vesicles.

Subject-reported adverse events, worsening of a pre-existing condition/disease/symptom or changes to concomitant medications will be recorded.

De-identified photographs of site reactions may be taken at the discretion of the Investigator and will not be reviewed or collected by the study sponsor.

10.4 Visit 4: Day 7-8 and Visit 5: Day 10-14

10.4.1 Tape and Polyester Chip Sites Irritation

Unresolved tape and or polyester chip induced irritation will be evaluated.

Tape irritation will be evaluated according to the following score scale:

None:	No erythema or other sign of irritation
Weak:	Faint to definite pink erythema
Moderate:	Moderate erythema, definite redness
Strong:	Severe erythema, very intense redness

Polyester chip induced irritation will be evaluated according to the following score scale:

None:	No erythema or other signs of irritation
Weak:	Faint to definite pink erythema at all polyester chip sites*
Moderate:	Moderate erythema, definite redness at all polyester chip sites*
Strong:	Severe erythema, very intense redness at all polyester chip sites*

Any response that is greater in severity than a strong irritation response may be graded as a potential allergic response as follows:

- 1+ Palpable erythema, moderate edema/ infiltrate, few papules, no vesicles. Weak reaction
- 2+ Strong infiltrate, numerous papules, possibly few vesicles present. Strong reaction
- 3+ Coalescing vesicles, bullae or ulceration. Extreme reaction

*To ensure that response to skin contact with the polyester chip is not confused with an allergic response to a specific allergen, all of the polyester chip sites per panel must present with the same or nearly the same response score.

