- Sensitive subjects (those who have had a past positive patch test to at least one of the dilution series allergens) may be tested with the allergen panels(s) and corresponding reference allergen(s) (with the exception of subjects enrolled in Germany who will not be tested with the reference allergens) to which they have had a previous response.
 - The Investigator will use his or her experience and medical expertise to determine if a subject with a past positive patch result should be tested to all dilution series allergens or only to the allergen to which the subject has had the past response.
 - Subjects with a past positive response to copper, zinc, tin, manganese or molybdenum will be tested with the panel containing the past positive response allergen plus the other allergen(s) located on the same panel. Specifically, Panel 2 contains copper, zinc and tin, and Panel 3 contains manganese and molybdenum. Hence, subjects with a past positive response to one of the allergens on the panel will also be tested with the other allergen(s) located on the same panel. It will not be necessary to test the additional reference allergens.
- Subjects with suspicion of metal contact allergy potentially associated with a metal implant will be tested with all dilution series and reference allergens.
- All subjects will be tested with the excipient controls on Panel 6. The Investigator will use his or her experience and medical expertise to determine if a subject with a strong suspicion of metal contact allergy who has not undergone previous patch testing will benefit from being patch tested with the four common allergens (nickel, chromate, cobalt and gold) in order to provide the individual with a complete diagnosis of metal contact allergy. Should the Investigator decide that testing with the four common allergens will not be of benefit to the subject, the Investigator will cut Panel 6 as illustrated in Figure 9, (Section 11.1, Investigational Allergen Panels) before applying the panel.

10.2 Visit 2: Day 2

Prior to removal of the investigational allergen and reference panels, tape adhesion will be evaluated and scored according to the following adhesion scale:

Excellent:	Skin contact good; all tape edges adherent; all allergens in contact with the skin
Good:	Skin contact acceptable; some tape edges lifting; all allergens in contact with the skin
Poor:	Little to no skin contact with panel; one or more allergens not in contact with the skin

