Detached:	Panel completely off the skin; none of the allergens in contact with the skin

If adhesion is 'Poor' or 'Detached' the allergen sites that were not in contact with the skin at the time of panel removal will be identified.

Patches that do not remain in place (completely detached) for the intended wear period (approximately 48 hours or two days) will not be replaced. The subject will be asked to return for follow-up visits until all patch sites reactions have resolved but data from this subject will not be included in the analysis of positive responses necessary to determine optimal dose.

Subjects whose patches are not worn for the intended wear period may return to be retested after 3 weeks at the discretion of the Investigator providing the skin site remains free of conditions that may affect test results.

Factors such as oily skin, excess hair, wet panel, sweat/skin moisture, and activity-associated failure, which may potentially contribute to poor adhesion, will also be captured on the data collection form.

The patch panels will be removed and time documented. There will be at least a 15-minute wait between patch removal and the irritation evaluations. Following the 15-minute wait, tape sites (entire panel minus the chip sites) then the polyester chip sites will be evaluated for skin irritation.

[figure not shown]
Skin irritation will be documented as follows:

- Panels 1-6: Irritation attributed to the adhesive used to adhere the panels to the skin (tape irritation) will be documented if the site of the entire panel with the exception of the chip sites, as shown below in Figure 5, shows signs of irritation
- Panels 1-6: Irritation attributed to the gel chips will be documented if all chip sites show signs of irritation. Note: To ensure that irritation resulting from skin contact with the polyester chip is not confused with an allergic response to a specific allergen, all of the polyester chip sites must present the same or nearly the same degree of irritation.
 - Panel 1: Chips on positions 1-4 and 7-10 will be evaluated for irritation
 - Panel 2: Chips on positions 1-12 will be evaluated for irritation
 - Panel 3: Chips on positions 1-4 and 7-10 will be evaluated for irritation
 - Panel 4: Chips on positions 1-12 will be evaluated for irritation
 - Panel 5: Chips on positions 1-4 and 7-10 will be evaluated for irritation

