The lead chemist in the department of pharmaceutical development at SmartPractice Denmark is responsible for the randomization of allergens on panels 1-5. The allergens will be randomized within each panel into three different configurations, per standard protocol. The different allergen configurations will be randomly assigned to subjects as they enter the study. The investigators and subjects will be aware of the allergens and the patch test doses on the test panels but will not be aware of the placement of the allergens on the individual panels (the different panel configurations). The key to the randomization scheme will be kept confidential at SmartPractice Denmark until it is forwarded to data management for analysis of the study results following completion of all study related procedures.

The allergens on panel 6 will not be randomized into different configurations. Should the Investigator elect to omit the common allergens from an individual's patch testing, the panel should be cut as shown below in Figure 9.

Figure 9: Panel 6 Configuration and Cutting Instructions

Unused portion of the panel is not to be discarded.

The remaining portion of the panel must be applied as it contains the excipient and blank patch controls. Scores for the blank (Position 4), PVP (Position 8), and HPC (Position 9) patches will be recorded in the case report forms as originally intended, in fields for positions 4, 8 and 9. Positions 1, 2, 3 and 7 will be documented in the case report form as 'not applied'.

All investigational products used in this study must be accounted for. Records must show amount and date of delivery of all test materials to the investigator. Likewise dates, amount, and signatures should document return of unused test panels. Product deliberately and/or accidentally destroyed by the investigator must also be documented.

The use of the investigational product for the individual subject, including number and identification of specific panels applied, application (or not) of common allergens and date and time of application and removal will be documented.

The following investigational panels with ascending doses of allergen and an excipient control will be used in this study.

Panel 1 Aluminum Dilution Series

Allergen	Excipients	Ascending Dosages (mg salt/cm ²)	Randomized Among Positions
Aluminum chloride hexahydrate	Water, Ethanol (99.9%), PVP	0.040, 0.12, 0.36, 0.72	1-4 and 7-10

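### On Panels 1, 4 and 5 the all-chips-alike rule cannot separate a polyester-chip response from a uniform reaction to the panel's only metal

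*Protocol*

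**What the plan says.** Protocol 10.2 sets the rule at patch removal: "Panels 1-6: Irritation attributed to the gel chips will be documented if all chip sites show signs of irritation". A note there requires a closely similar degree of irritation at all the sites, so that a chip effect is not mistaken for allergy to a particular allergen. Section 10.3.1 carries the rule to Visit 3. Section 10.4.1 carries it to Visits 4 and 5, judged panel by panel: "all of the polyester chip sites per panel must present with the same or nearly the same response score". It adds a graded scale of 1+ to 3+: "Any response that is greater in severity than a strong irritation response may be graded as a potential allergic response as follows". Section 10.6 allows a similar reading after Visit 6.

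The metal-free patches (blank, PVP, HPC) are all on Panel 6. Section 10.1 says "All subjects will be tested with the excipient controls on Panel 6". When the common allergens are cut away, 11.1 says "The remaining portion of the panel must be applied as it contains the excipient and blank patch controls". No text on the chip rule refers to these patches.

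The result feeds the first secondary safety item in Protocol 7.2 and SAP 4.2, the frequency of tape and chip irritation or allergic reactions over Visits 2 to 6. SAP 6.2 tabulates it without any further derivation.

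**The concern.** Uniformity across a panel points to the chip only if the chips differ in everything except the polyester carrier. That holds on Panels 2 and 3, which carry three metals and two metals. It does not hold on Panels 1, 4 and 5, where the metal is as common to all chips as the polyester is.

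What is at stake is the meaning of one safety frequency. A reaction to aluminum, titanium or vanadium could be reported as a reaction to the polyester carrier, a component shared by all the T.R.U.E. Test panels. The design already holds the patches that could tell the two apart, but the rule does not use them.

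**Working it through.** The plan states no figure on this point, so there is none to reproduce. The check sets the positions assessed in Protocol 10.2 (for example, "Panel 1: Chips on positions 1-4 and 7-10 will be evaluated for irritation") against the contents in the 11.1 tables (for example, aluminum chloride at "0.040, 0.12, 0.36, 0.72" mg salt/cm²).

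**Step 1: contents of the assessed chips**

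| Panel | Chips assessed | Contents | Metals | Metal-free chips |
|---|---|---|---|---|
| 1 | 8 | 2 aluminum salts × 4 doses = 8 | 1 | 0 |
| 2 | 12 | copper, zinc, tin × 4 doses = 12 | 3 | 0 |
| 3 | 8 | manganese, molybdenum × 4 doses = 8 | 2 | 0 |
| 4 | 12 | 4 titanium salts × 3 doses = 12 | 1 | 0 |
| 5 | 8 | 2 vanadium salts × 4 doses = 8 | 1 | 0 |
| 6, uncut | 7 | 4 common allergens + blank, PVP, HPC | 4 | 3 |

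On Panels 2 and 3 a reaction to one metal covers at most 4 of 12 or 4 of 8 chips, so it fails the rule, as intended. On Panels 1, 4 and 5 a reaction to the metal can cover every assessed chip.

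**Step 2: how alike the metal sites would have to be** (highest dose ÷ lowest dose)

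- Panel 1, by salt weight: chloride 0.72/0.040 = 18.0; lactate 0.84/0.047 = 17.9; across the panel 0.84/0.040 = 21.0.
- Panel 4, by titanium: each salt 4.0 (for example 0.22/0.055); across the panel 0.28/0.055 = 5.1.
- Panel 5, by vanadium: each salt, and the panel, 0.050/0.0042 = 11.9.

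Similar scores at every site are therefore easiest to reach on Panel 4 and hardest on Panel 1.

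**Step 3: two subjects under the rule.** Subject A reacts to polyester. Subject B reacts to titanium at all 12 sites to a similar degree. On Panel 4 both meet the rule and both are entered as chip responses. On Panel 6 they differ: A's blank patch should react and B's should not. The rule, applied per panel, does not make that comparison. Under 10.1, a subject with a past positive test may wear only the panel for that metal plus the Panel 6 controls, so Panel 6 may be the only other investigational panel to compare with.

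**Step 4: which visits are exposed.** In Figure 2 chip irritation is assessed at Visit 2, while skin-reaction scoring starts at Visit 3. At Visit 2 a uniform early metal response on these panels has only the chip field to go into. From Visit 3, site scores exist for the allergen and the control patches. From Visit 4, the 1+ to 3+ chip descriptions closely match the allergen-site criteria in Figure 6, so morphology does not separate the two either.

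**The case against.** The strongest reply is that chip and allergen-site responses are recorded in parallel (10.3.1 with 10.3.2, 10.4.1 with 10.4.2), so nothing is lost from the primary endpoint. This stands. A reader might infer that subjects who react at every dose are credited to the chip and drop out of the 15-subject count, moving the selected dose. The documents do not support that. Section 10.6 makes a site positive on a score of 1+ to 3+ at any of Visits 3 to 6, and no text lets a chip entry cancel a site score. SAP 6.1 drops only completely detached patches from the dose analysis, and missing determinations from concordance.

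Second, the rule is partly permissive. In 10.4.1 uniformity is a necessary condition, the section follows up unresolved irritation, and the allergic grades are optional there and in 10.6. This also stands, and it limits the claim about chip allergy. It does not reach 10.2, where uniform irritation is to be documented as chip irritation.

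Third, 28 of the 48 dilution-series chips (28/48 = 58%) sit on these three panels. A reader might take that as a misclassification rate. It is only a share of chips. Similar scores over a 12- or 21-fold dose range may be rare.

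Fourth, Panel 6 is itself assessed for chip irritation, and its control patches are scored as sites, so an analyst could make the comparison. True, but neither document requires it or says how to do it.

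Finally, a negative blank alone would not settle the source. The blank carries no excipient, whereas Panels 1 and 4 use PVP and Panel 5 uses HPC. A reaction to the gel would leave the blank negative. The remedy must allow for this.

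**Conclusion.** The point holds for the safety endpoint. On Panels 1, 4 and 5 (8, 12 and 8 chips, none metal-free) the rule as written cannot tell a polyester-chip response from a uniform metal response, so the reported chip irritation or allergy frequency can include metal reactions. Visit 2 is the clearest case.

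The size of the error cannot be computed, because the documents give no frequency of uniform reactions. The only ordering they support is by dose range, with Panel 4 the most exposed and Panels 5 and 1 less so. That ordering assumes that similar scores are more likely over a narrower range of dose.

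The effect is confined to one descriptive secondary frequency. No effect on dose selection is shown.

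**What to change.** In Protocol 10.2, 10.3.1, 10.4.1 and 10.6, and in the SAP derivation of the chip endpoint, read a uniform response on Panel 1, 4 or 5 against the Panel 6 controls:

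- **Blank (position 4) reacts similarly:** count a polyester-chip response.
- **Blank negative, matching excipient patch reacts** (PVP for Panels 1 and 4, HPC for Panel 5): label it an excipient or gel response.
- **Both negative:** do not count it as a chip response.

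State that allergen-site scores stand as recorded in every case.

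Apply the derivation to recorded site scores from Visit 3. Define which control-site scores count as a match, because the scales differ. The chip scale runs from none to strong, the Visit 3 site scale includes doubtful and irritant, and 10.4.2 and 10.5 list only negative and 1+ to 3+.

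For Visit 2, either add a site-level entry for the three control patches or report chip irritation on Panels 1, 4 and 5 as not separable from metal irritation. If Visit 2 data are already collected, only the second option remains.

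The cost is wording in four protocol sections, one SAP derivation and, if chosen, a small data-field addition at Visit 2. Fewer events will be labelled chip reactions. SAP section 1 places finalization before database lock, so the derivation can still be fixed in advance if the database is not yet locked.

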10.4.2 Allergic Skin Responses

Allergen sites will be examined for the presence of erythema, infiltration, papules, discrete vesicles and bullous reactions and scored as follows: (-) negative, (1+) weak positive reaction, (2+) strong positive reaction, and (3+) extreme positive reaction.

All reactions (scores of 1+, 2+ or 3+) will be categorized as either late or persistent. Persistent reactions will be further clarified as either persistent-healing or persistent-escalating.

Definitions:

Late Reaction: A reaction that initially appears at day 7-14 after application of panels.

Persistent Reaction: A reaction that initially appears at day 2-4 and persists through day 7-21 or beyond.

Persistent-Healing: A persistent reaction that has not worsened since the previous evaluation, remains the same or appears to be healing.

Persistent-Escalating: A persistent reaction that has worsened since the previous evaluation

Subject-reported adverse events, worsening of a pre-existing condition/disease/symptom or changes to concomitant medications will be recorded.

De-identified photographs of site reactions may be taken at the discretion of the Investigator and will not be reviewed or collected by the study sponsor.

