7.2 Secondary Endpoint

Determination of allergen safety

- Frequency of tape and polyester chip induced irritation or allergic reactions at Visits 2 through 6.

- Frequency of subject reported sensations of itching and/or burning for each allergen panel at patch removal.
- Frequency of positive (1+, 2+, 3+) skin reactions for each investigational and reference allergen dose at each post removal visit and overall.
- Frequency of negative, doubtful, irritant, late and persistent skin reactions for each investigational and reference allergen dose at each post removal visit (late and persistent reactions at visits 4, 5 and 6 only).
- Frequency of all adverse events. Documentation for all local and systemic adverse reactions classified by the investigator as possibly or definitely related to the study product (e.g., erythema, hyper-pigmentation, hypo-pigmentation, skin thinning or dermatitis flare) will include grade (mild, moderate or severe) and time point (clinic visit).

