8.0 STUDY DESIGN

8.1 Overview

This is a prospective, multi-center, randomized, double-blind design. That is, the allergen doses on each panel will be randomized into three different configurations, which will be randomly assigned to subjects as they enter the study. Although the investigators and subjects will know which allergen is being tested, they will be blinded to the placement of the allergen doses within each panel. A 48-hour application (approximate) of investigational allergen panel(s), an excipient control and corresponding reference petrolatum (or aqueous) allergen(s) will be applied to the skin of human subjects to test for potential positive allergic responses. Test sites will be evaluated at 3-4, 7-8, 10-14 and 19-23 days after application. The chosen evaluation times are consistent with generally accepted international patch test guidelines and are designed to prevent missed late reactions and false negatives. The final clinic visit (day 21) allows the investigator to evaluate any late or persistent localized reactions. The investigator may choose to perform this visit via telephone if there are no residual reactions. If there are persistent escalating reactions noted at Visit 6, the investigator will determine and record follow up action.

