2. Categorize the skin reactions at each site as either negative or positive. No skin reaction scores (1+, 2+ or 3+) assigned to during any of the reaction assessment visits, (Visits 3-6) would constitute a negative reaction. A positive skin reaction is defined as an assigned score of 1+, +2 or 3+ during at least one of the reaction assessment visits (Visits 3-6).

[figure not shown]

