4.2 Secondary Endpoint (Safety)

Determination of allergen safety:

- Frequency of tape and polyester chip induced irritation or allergic reactions at Visits 2 through 6.
- Frequency of subject reported sensations of itching and/or burning for each allergen panel at patch removal.
- Frequency of positive (1+, 2+, 3+) skin reactions for each investigational and reference allergen dose at each post removal visit and overall.

STATISTICAL ANALYSIS PLAN

Date : 30 NOV 19

Version: 01

Product Name:

Sponsor Study No.: SP 14 8MP 201 Metal Allergen Epicutaneous Patch

- Frequency of negative, doubtful, irritant, late and persistent skin responses for each investigational and reference allergen dose at each post removal visit (late and persistent reactions at visits 4, 5 and 6 only).
- Frequency of all adverse events. Documentation for all local and systemic adverse reactions classified by the investigator as possibly or definitely related to the study product (e.g., erythema, hyperpigmentation, hypo-pigmentation, skin thinning or dermatitis flare) will include grade (mild, moderate or severe) and time point (clinic visit).

5. Statistical Considerations

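### Doubtful and irritant reactions are required by dose at every post-removal visit, but the scale written for Visits 4 to 6 has no grade for either

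*Protocol*

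**What the plan says.** Protocol Section 8.1 sets four readings: "Test sites will be evaluated at 3-4, 7-8, 10-14 and 19-23 days after application". These are Visits 3, 4, 5 and 6.

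At Visit 3 (Section 10.3.2) each site is scored "Neg) negative; (IR) irritant reaction; (?) doubtful reaction; (1+) weak positive reaction; (2+) strong positive reaction; or (3+) extreme positive reaction". Figure 6 in the same section describes each grade.

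At Visits 4 and 5 (Section 10.4.2), sites are "scored as follows: (-) negative, (1+) weak positive reaction, (2+) strong positive reaction, and (3+) extreme positive reaction". Section 10.5 gives the same four grades for Visit 6 when it is held in the office.

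The safety endpoint in protocol Section 7.2 includes "Frequency of negative, doubtful, irritant, late and persistent skin reactions for each investigational and reference allergen dose at each post removal visit". A bracket after it restricts late and persistent reactions, and only those, to Visits 4, 5 and 6. Protocol Sections 4.8, 4.15 and 12.1 repeat the requirement. SAP Section 4.2 carries it over as "Frequency of negative, doubtful, irritant, late and persistent skin responses for each investigational and reference allergen dose at each post removal visit", and SAP Section 6.2 lists it again among the analyses. SAP Section 3.5 declares no change from the protocol analysis.

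**The concern.** The endpoint asks for two response categories at visits where the written scale does not offer them. The bracket shows that the authors considered visit limits for this item and set none for doubtful or irritant.

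The study compares the safety of ascending doses, and irritation at an individual dose site is part of that comparison. If the scale is followed literally, the Visit 4 to 6 tables will show no doubtful or irritant reactions at any dose. A reader of the report could not tell a true absence from a category that was never offered. A dose with irritation that outlasts Visit 3, or first appears after it, would look the same as one without.

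**Working it through.** The plan states no figure on this point, so the check compares the grades offered with the categories required, and then counts.

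**1. Grades offered against categories required**

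| Reading | Grades offered at an allergen site | Doubtful and irritant required? | Can they be scored? |
|---|---|---|---|
| Visit 3 (10.3.2) | negative, IR, doubtful, 1+, 2+, 3+ | yes | yes |
| Visit 4 (10.4.2) | negative, 1+, 2+, 3+ | yes | no |
| Visit 5 (10.4.2) | negative, 1+, 2+, 3+ | yes | no |
| Visit 6, office (10.5) | negative, 1+, 2+, 3+ | yes | no |

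No section extends the Visit 3 scale to later visits.

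**2. Whether another record fills the gap**

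Sections 10.4.1 and 10.5 keep irritation scoring at Visits 4 to 6. It covers the tape area, or the polyester chips when all chip sites on a panel react alike. It cannot record irritation at one dose of one allergen. The SAP Section 5.2 derived-score rule mentions doubtful or irritant at Visit 3 only, and creates no such grade later.

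**3. Which available grade a doubtful or irritant site would receive**

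- Figure 6 defines negative as "Negative, no skin changes in the tested area". Neither faint erythema nor sharply limited inflammation meets that.
- Figure 6 defines 1+ by palpable erythema with oedema or infiltrate. A doubtful reaction is non-palpable and an irritant reaction lacks infiltrate, so neither meets 1+.

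Neither option fits. A reader who keeps to the 1+ criteria is left with negative.

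**4. Size**

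- Investigational doses (protocol Section 11.1, Panels 1 to 5): aluminum 8, copper 4, zinc 4, tin 4, manganese 4, molybdenum 4, titanium 12, vanadium 8. Sum = 48.
- Reference allergens (Section 11.2): aluminum 2, copper 1, manganese 1, molybdenum 1, tin 1, titanium 4, vanadium 2, zinc 1. Sum = 13.
- Preparations, leaving out Panel 6: 48 + 13 = 61.
- Doubtful or irritant frequencies required: 61 × 2 categories × 4 readings = 488.
- Supported by the written scale (Visit 3 only): 61 × 2 × 1 = 122.
- With no grade behind them: 488 − 122 = 366, and 366 / 488 = 75%.
- Whole endpoint item: 61 × (3 categories × 4 visits + 2 categories × 3 visits) = 61 × 18 = 1,098. The unsupported share is 366 / 1,098 = one third.

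**5. Reach into the primary endpoint**

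Section 10.6 states: "No skin reaction scores (1+, 2+ or 3+) assigned to during any of the reaction assessment visits, (Visits 3-6) would constitute a negative reaction". A doubtful or irritant site is therefore already negative in the final categorisation, including at Visit 3 where those grades exist. Writing negative for it at Visit 4, 5 or 6 leaves both the 15-subject count and the final negative/positive determination unchanged. Only grading it up to 1+ would change them.

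**The case against.** The strongest objection is that the documents show conflicting text and do not prove that the data went uncollected. The case report form and the table shells (a separate document under SAP Section 9) are not available. SAP Section 6.1 lists negative, irritant, doubtful and positive responses without limiting any to Visit 3. The form may have carried all six codes throughout. This stands as a limit on the conclusion, but Sections 10.4.2 and 10.5 would still be wrong and need correcting.

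Visit 3 is also the main reading for irritation. Section 6.11 says that mild irritant reactions have faded by 72 to 96 hours, and Section 8.1 gives the purpose of the reading times as avoiding missed late reactions and false negatives. A dose that irritates on Day 3-4 is therefore recorded as such. This stands in part: what is lost is the duration of irritation and any doubtful or irritant reaction first seen later. Section 10.3.1 provides for tape or chip irritation that persists beyond Visit 3, so the protocol does not assume that all irritation has gone by then. Related local reactions are also documented as adverse events with grade and visit, but that is not a systematic score of every site.

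Visit 6 may be completed by telephone when no reactions remain, so the practical loss there is smaller than the count suggests.

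A reader might infer that the by-visit safety frequencies as a whole cannot be produced. The documents do not support that. Positive, late and persistent reactions can be tabulated at Visits 4 to 6, and so can negative, though it may absorb the missing grades.

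A reader might also infer that dose selection and kappa are biased. That requires a reader to give 1+ to a site that does not meet the Figure 6 criteria, and nothing in Sections 10.4.2 or 10.5 relaxes those criteria. If it did happen at all of Visits 4, 5 and 6, SAP Section 5.2 would also turn a doubtful or irritant Visit 3 score into 1+. This is a possible misgrading, not a consequence of the plan as written.

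**Conclusion.** The inconsistency is real and stands in current text. As written, two categories named in a secondary safety endpoint can be scored at one of four readings. The other three would yield empty or zero frequencies by construction, which is 75% of the doubtful and irritant entries. The likely direction of error is to understate late or lingering irritation by dose, because such sites would most probably be recorded as negative.

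This assumes that the form followed Sections 10.4.2 and 10.5, and that readers kept to the Figure 6 definition of 1+. The count of 366 is of planned table entries. It does not say how many sites would have been doubtful or irritant late, and the documents give no basis for estimating that.

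The point should be fixed, but it does not threaten the primary analysis: it concerns two descriptive categories of a secondary endpoint, and Section 10.6 shields the final positive/negative determination.

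**What to change.** Reconcile protocol Sections 10.4.2 and 10.5 with protocol Sections 4.8, 4.15, 7.2 and 12.1 and SAP Sections 4.2 and 6.2, in one of two ways.

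1. If data can still be collected, or the form already carried all six codes, replace the four-grade list in Sections 10.4.2 and 10.5 with the Figure 6 six-grade scale. The cost is protocol wording and, where needed, two extra codes on the form. No visit, reader or procedure is added.
2. If Visits 4 to 6 were captured on four grades, state in SAP Sections 4.2 and 6.2 that doubtful and irritant frequencies exist for Visit 3 only. Print 'not assessed' instead of 0% at Visits 4 to 6, and footnote that negative at those visits may include doubtful or irritant sites. The cost is SAP and table wording.

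Checking the form shows which route applies.
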